## **5.6 OTHER ASSESSMENTS**

Not applicable.

## **5.7 APPROPRIATENESS OF MEASUREMENTS**

All measurements conducted in the trial are using standard methods.

## 6. INVESTIGATIONAL PLAN

### 6.1 VISIT SCHEDULE

This trial starts with Visit 0 during which informed consent process shall be undergone HRCT scans and biopsies (later if available) shall be sent for central review to confirm the diagnosis of IPF. Further the trial consists of screening visit (Visit 1) and screening period lasting 14 days (2 weeks), treatment period lasting 52 weeks and follow-up period lasting 28 days (4 weeks). The treatment period will consist of two parts. At Visit 2 patients will be randomised into double-blind portion of the study. Additional clinic visits of the double blind period will be scheduled at week 4, 8 and 12 (Visits 3, 4 and 5). At Visit 5, i.e. after completing the randomised, double blind treatment all patients will enter the single arm, open label, active treatment period. During this period patients will visit the clinic for scheduled visits at week 16, 20, 24, 36 and 52 (Visits 6, 7, 8, 9 and 10). The follow-up visit (Visit 11) will be scheduled 28 days post-treatment. Unscheduled visits may be conducted anytime if deemed necessary.

Time windows to be adhered to for scheduling of visits are shown in the [Flow Chart](#). Sites should make every attempt to adhere to the protocol time windows as close as possible. The screening period (between Visit 1 and Visit 2) may be extended by additional 2 weeks (i.e. 28 day total) for any reasons (e.g. exacerbation, lab results receipt, etc.). All onsite visits from Visits 1 to Visit 11 will be scheduled in the morning, in order to guarantee start of pulmonary function testing at approximately the same time of the day (recommended time for PFTs from 8:00 till 11.00 a.m.; any subsequent PFTs should preferably be done within  $\pm 90$  minutes from the measurement at Visit 1). Patients should make every attempt to complete the study as specified. Investigators should encourage patient treatment compliance and adherence to other protocol specific activities.

All deviations from the planned visit schedule will be documented.

Rescheduling prior to randomisation.

- if a patient experiences acute IPF exacerbation or respiratory tract infection between Visit 0 and Visit 1, the Visit 1 will be postponed until complete recovery from the infection or exacerbation, preferably 4 weeks following the recovery from the infection or exacerbation.
- laboratory parameters found abnormal at visit 1 may be re-tested once prior to Visit 2.
- if the screening period (2 weeks and 2 additional weeks for administrative reasons) needs to be extended further (counted from Visit 1), the clinical monitor should be contacted. Reasoned prolongation of the screening period may be allowed by the clinical monitor.
- if a patient experiences an IPF exacerbation or respiratory tract infection during the screening period (2 weeks) between Visit 1 and Visit 2, the Visit 2 will be postponed until complete recovery from the infection or exacerbation, preferably 4 weeks following the recovery from the infection or exacerbation.

Patients should make every attempt to adhere to the protocol. Investigators should encourage patient treatment compliance and adherence to other protocol related activities.

Subsequent visits should always be planned to take place at scheduled dates in line with the protocol [Flow Chart](#).

## 6.2 DETAILS OF TRIAL PROCEDURES AT SELECTED VISITS

### 6.2.1 Screening and run-in period(s)

#### Visit 0

Informed consent will be obtained prior to patient participation in the trial, which includes any study related procedures, medication washout procedures or restrictions. Furthermore, the patient will be asked to give informed consent to the pharmacogenomic (optional DNA and serum banking sample) analyses. HRCT and biopsy tissue samples (later if available) shall be sent for central review. Call the IRT to register a new patient into the study.

#### Visit 1

Visit 1 may only be performed once the central HRCT and biopsy tissue sample reading confirm the IPF diagnosis

At Visit 1:

- Verify medication washout compliance
- Record demographic data
- Conduct relevant medical history and physical examination including height and weight measurements, vital signs (blood pressure and pulse rate), pulse oximetry (SpO2) and 12-lead ECG. The vital signs (seated), pulse oximetry and ECG should be conducted following five minutes rest and prior to screening pulmonary function testing and DLCO measurement
- Perform blood collections for haematology, serum chemistry, coagulation panel and urine pregnancy test (if applicable). *Blood samples shall be sent to central laboratory; for further information refer to Laboratory Manual in the ISF*
- Perform **pulmonary function testing** in the morning preferably between 08:00 – 11:00. Patients must demonstrate FVC ≥ 80% to be eligible.
- Perform DLCO measurement
- Review and record all adverse events experienced since signed informed consent
- Record concomitant therapy for the previous 3 months in the eCRF as described in [Section 4.2](#).
- Review inclusion and exclusion criteria
  
- Instruct and train patients on how to perform and record PFTs at home
- Give instructions on medication restrictions and washout requirements for the screening period and subsequent visits
- Instruct patients to bring all study-related equipment to the clinic at each visit
- Schedule the next clinic visit in 14 days (2 weeks), additional 2 weeks are allowed for administrative reasons

#### Screening period

## 6.2.2 Treatment period(s)

The order of procedures should be as follows: patient self-administered questionnaires (if applicable), blood collections (as per [Flow Chart](#)), vital signs and ECG (if applicable), PFTs, medication administration (if applicable).

### Observations / Procedures

#### Visit 2 (randomisation visit)

*Optional* - Call the patient the day before the clinic visit to remind the clinic visit next day. Remind the patient medication washout requirements (if applicable) and to bring all study related supplies (home spirometer) to the clinic visit.

- Review and record all adverse events experienced and changes in concomitant therapy.
- Review all inclusion and exclusion criteria
- Perform blood collections for haematology, serum chemistry, coagulation panel and urine pregnancy test (if applicable) including biomarker serum and plasma samples, biomarker RNA sample, optional serum banking sample and optional DNA banking sample if applicable (later sample may be collected at any time as of Visit 2). For further details on safety lab collections refer to [Section 5.3.3](#). For further details on biomarker related collections refer to [Section 5.5](#). *Blood samples shall be sent to central laboratory; for further information follow Laboratory Manual in the ISF*
- Record vital signs (blood pressure and pulse rate) before PFTs and with the patient seated and rested for at least five minutes
- Record patient weight
- Perform supervised PFTs
- Perform randomisation in case patient is eligible
- Call IRT to randomise the patient and dispense the first blinded medication kit (period between Visit 2 and Visit 3)

- Instruct patient to take the first capsule at the clinic under trial staff supervision. Refer to [Section 4.1.4](#). Instruct patient on further medication intake, please refer to [Section 4.2](#) regarding possible dose reductions, interruptions and management of drug related AEs
- Dispense the Patient Diary and instruct the patient on its use
- Schedule next planned clinic visit. Instruct patients to bring all study related treatments to the next clinic visit

### **Visits 3 and 4**

*Optional* - Call the patient the day before the clinic visit to remind the clinic visit next day. Remind the patient medication washout requirements (if applicable) and to bring all study related supplies (home spirometer, patient diary, treatments, etc.) to the clinic visit.

- Review and discuss new Patient Diary entries with the patient
  - Review and record all adverse events experienced and changes in concomitant therapy
  - Perform blood collections and urine pregnancy test (if applicable). Refer to [Section 5.3.3](#)
  - Collect biomarker serum and plasma samples, optional serum banking sample and optional DNA banking sample if applicable (later sample may be collected at any time as of Visit 2). Refer to [Section 5.5](#)
- 
- Record vital signs (blood pressure and pulse rate) before PFTs and with the patient seated and rested for at least five minutes (at Visit 3 only)
  - Record patient weight
  - Perform supervised PFTs
  - Perform Study Drug Compliance Check
  - Call IRT to dispense the blinded medication kits (for further details refer to [Section 4.1.4](#))
  - Administer morning dose of the trial drug from newly dispensed kit at the site
  - Schedule next planned clinic visit. Instruct patients to bring all study related treatments to the next clinic visit

## **Visit 5**

Optional - Call the patient the day before the clinic visit to remind the clinic visit next day. Remind the patient medication washout requirements (if applicable) and to bring all study related supplies ( , patient diary, treatments, etc.) to the clinic visit.

- Review and discuss new Patient Diary entries with the patient
- Review and record all adverse events experienced and changes in concomitant therapy
- Record vital signs (blood pressure and pulse rate) before PFTs and with the patient seated and rested for at least five minutes
- Record patient weight
- Perform safety laboratory collections and urine pregnancy test (if applicable). For further details refer to [Section 5.3.3](#)
- Collect biomarker serum and plasma samples, optional serum banking sample and optional DNA banking sample if applicable (later sample may be collected at any time as of Visit 2). Refer to [Section 5.5](#)

### [Section 5.5](#)

- Perform supervised PFTs
- Perform Study Drug Compliance Check
- Call IRT to dispense the open label medication kits (for further details refer to [Section 4.1.4](#))
- Instruct patient to take the first capsule of open label medication at the clinic under trial staff supervision. Refer to [Section 4.1.4](#) Instruct patient on further medication intake, please refer to [Section 4.2](#) regarding possible dose reductions, interruptions and management of drug related AEs.
- Schedule next planned clinic visit. Instruct patients to bring all study related treatments to the next clinic visit.

## **Visits 6, 7, 8 and 9**

Optional - Call the patient the day before the clinic visit to remind the clinic visit next day. Remind the patient medication washout requirements (if applicable) and to bring all study related supplies ( , patient diary, treatments, etc.) to the clinic visit.

- Review and discuss new Patient Diary entries with the patient
- Review and record all adverse events experienced and changes in concomitant therapy

- Record vital signs (blood pressure and pulse rate) before PFTs and with the patient seated and rested for at least five minutes (Visit 6, 8 and 9)
- Record patient weight
- Perform safety laboratory collections and urine pregnancy test. For further details refer to [Section 5.3.3](#).
- Collect biomarker serum and plasma samples, optional serum banking sample and optional DNA banking sample if applicable (later sample may be collected at any time as of Visit 2). Refer to [Section 5.5](#)

- Perform supervised PFTs.
- Perform Study Drug Compliance Check
- Call IRT to dispense the open label medication kits (for further details refer to [Section 4.1.4](#)) (not applicable at Visit 6 and 7)
- Administer morning dose of the trial drug from the newly dispensed kits at the site (not applicable at Visit 6 and 7, as kits dispensed at Visit 5 will be used at these visits)
- Schedule next planned clinic visit. Instruct patients to bring all study related treatments to the next clinic visit

### **Visit 10 (End of treatment visit)**

Optional - Call the patient the day before the clinic visit to remind the clinic visit next day. Remind the patient medication washout requirements (if applicable) and to bring all study related supplies (home spirometer, patient diary, treatments, etc.) to the clinic visit.

- Review and discuss new Patient Diary entries with the patient
- Review and record all adverse events experienced and changes in concomitant therapy
- Perform blood collections for haematology, serum chemistry, coagulation panel and urine pregnancy test (if applicable), including biomarker serum and plasma samples, biomarker RNA sample, optional serum banking sample and optional DNA banking sample if applicable (later sample may be collected at any time as of Visit 2). For further details on safety lab collections refer to [Section 5.3.3](#). For further details on biomarker related collections refer to [Section 5.5](#). *Blood samples shall be sent to central laboratory; for further information follow Laboratory Manual in the ISF.*

- Perform physical examination including vital signs (blood pressure and pulse rate) and perform 12-lead ECG before PFTs with the patient seated and rested for at least five minutes.
  - Record patient weight
  - Perform supervised PFTs
  - Perform Study Drug Compliance Check
  - Administer the last morning dose of the trial drug at the site. Collect remaining study drug. After the last dose of trial medication the Investigator / the treating physician may initiate further IPF treatment in line with the protocol [Section 4.2.2](#).
  - Call IRT to record End of Treatment
- 
- Schedule next planned clinic visit (the Follow-up visit). Instruct patients to bring all remaining study supplies to the next clinic visit

### 6.2.3 Follow Up Period and Trial Completion

#### Visit 11 (Follow-up Visit)

Patients will be contacted once at the end of the follow up period. Adverse events and concomitant therapies will be reviewed and recorded. Urine pregnancy test will be performed in applicable patients. A 12-lead ECG and physical examination including vital signs should be performed if these were abnormal at Visit 10. Remaining trial supplies should be collected.

#### Premature withdrawal

Patients who prematurely discontinue study drugs (refer to [Section 3.3.4](#)) before the planned end of treatment at Visit 10, should come to the clinic as soon as possible after last drug intake for an early EOT visit. Reason for discontinuation must be documented in the eCRF. For detailed description of the trial procedures at this visit, please refer to the [Flow Chart](#).

In addition patients will be invited to attend all remaining planned visits and perform all study procedures. If a patient doesn't accept to attend remaining study visits, collect the home spirometer and any trial related supplies and contact patient for vital status collection at week 52. The need to come to remaining scheduled visits in case of prematurely discontinuation of trial medication will be explained to patients prior to their participation in the trial.

Vital status information

In case of an early discontinuation of trial medication, if the patient does not agree to come to future visits as planned, any attempt will be made to get information on vital status at Week 52 (refer to [Flow Chart](#)).

Patients will be asked to agree to be contacted by the site personnel, which could be by telephone calls, to allow collection of this information.

If death occurs, the investigator will review the circumstances, including the relevant medical records to ascertain the most likely primary and secondary causes of death.

Collection of vital status will be performed in accordance with national ethical and regulatory guidelines. The need for vital status information will be explained to patients prior to their participation in the trial.

## 7. STATISTICAL METHODS AND DETERMINATION OF SAMPLE SIZE

### 7.1 STATISTICAL DESIGN - MODEL

This is a randomised, placebo controlled, multi-centre, multinational, prospective, double blind trial to investigate the effect of oral nintedanib 150 mg twice daily on change in biomarkers of extracellular matrix (ECM) turnover in patients with idiopathic pulmonary fibrosis (IPF) and preserved forced vital capacity (FVC).

The primary endpoint is the rate of change (slope) in blood CRPM from baseline to week 12. Therefore, the rate of change (slope) in blood CRPM will be analyzed using random coefficient regression (random slopes and intercepts) model including gender, age and height as covariates.

The secondary endpoint, proportion of patients with disease progression defined by FVC decline  $\geq 10\%$  or death, will be analysed using logistic regression models or other appropriate methods.

### 7.2 NULL AND ALTERNATIVE HYPOTHESES

The objective of this study, demonstrating a treatment effect of nintedanib at a dose of 150 mg bid compared to placebo for the rate of change (slope) in blood CRPM, will be tested using the following null hypothesis.

$H_0$ : No difference in the rate of change (slope) in blood CRPM evaluated from baseline until 12 weeks of treatment between nintedanib mg bid and placebo.

The alternative hypothesis is

$H_a$ : The rate of change (slope) in blood CRPM is different for patients taking nintedanib 150 mg bid than those taking placebo.

The hypothesis will be tested using 5% level of significance (two-sided test).

### 7.3 PLANNED ANALYSES

The statistical analysis will be based on the following populations.

#### **Treated Set (TS):**

The treated set (TS) consists of patients who are randomised to a treatment group and receive at least one dose of study medication

#### **Randomised Set (RS):**

The Randomised set (RS), consists of those patients who were randomised to a treatment group.

The efficacy and safety analysis will be conducted on the TS. Efficacy parameters will be analysed from an as randomised perspective and safety parameters from an as treated perspective, respectively. For efficacy analysis, all measurement performed within the first 12 weeks will be used. Efficacy evaluations done after lung transplant will not be used for the efficacy analyses; sensitivity analyses will be performed including these data.

Although there is no per protocol data set in the study, reasons for important protocol violations will be specified in the Trial Statistical Analysis Plan (TSAP). Patients with potential important protocol violations (those that relate to patient safety or efficacy) will be identified at Blinded Review Planning Meetings and listed in the clinical trial report.

### **7.3.1 Primary endpoint analyses**

The primary endpoint is the rate of change (slope) in blood CRPM evaluated from baseline over 12 weeks (expressed in ng/mL/month) estimated from measurements taken over 12 weeks of treatment. The rate of change (slope) in blood CRPM is assumed to be linear within each subject over the 12 weeks period. The intercepts and slopes will be assumed to be normally distributed with arbitrary covariance matrix. Gender, age and height which are usual predictors of FVC will also be included in the model. Baseline blood CRPM will be measured at visit 2. No imputation is planned if this assessment is not available for a patient. The within patient error will be assumed to be independent and normally distributed with mean zero and a common variance. The Kenward-Roger approximation will be used to estimate denominators degrees of freedom. Significance tests will be based on least-squares means using a two-sided  $\alpha=0.05$  (two-sided 95% confidence intervals). Analyses will be implemented using SAS® Version 9.4.

The linearity assumption for the rate of change (slope) in blood CRPM will be tested and sensitivity analysis will be done with alternative models described in the Trial Statistical Analysis Plan (TSAP). The effect of missing data will be investigated using pattern-mixture models. Depending on the pattern of the missingness in the data, multiple imputation methods may also be considered.

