## 7.6 RANDOMISATION

Patients will be randomised in blocks to double-blind treatment with an unequal probability 1 to 2 of assignment to nintedanib and placebo. BI will arrange for the randomisation and the packaging and labelling of trial medication. The randomisation list will be generated using a validated system, which involves a pseudo-random number generator so that the resulting treatment will be both reproducible and non-predictable. The block size will be documented in the CTR. Access to the codes will be controlled and documented. All members of the Medical Project Team will remain blinded to the randomisation schedule until after the final database is locked.

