## 7.7 DETERMINATION OF SAMPLE SIZE

The sample size calculations are based on change relative to baseline in biomarker levels of serum CRPM, serum C1M and serum C3M (unpublished data, no reference available). The sample size calculations are based on two-sided tests ( $\alpha = 0.05$ ) to detect a difference in means of two independent samples with a 1:2 randomisation ratio nintedanib:placebo in the samples with a power of 90%. No multiplicity adjustments are made as part of the power calculation, and no adjustment is made for a potential subject withdrawal. Sample size calculations are performed for assumed differences between treatment group and placebo of 20% and 30% difference. Due to the lack of data from respective IPF patients and since there is no evidence biomarker courses are principally different across both indications, data from two studies of RA patients are used to estimate the standard deviation over time in biomarker values relative to baseline: Study A) RA patients including a placebo group and a treatment group with measurements of serum CRPM, serum C1M and serum C3M at baseline, weeks 4, 16, and 24; and Study B) RA patients including a placebo group and a treatment group with measurements of serum CRPM, serum C1M and serum C3M at baseline, weeks 4, and 12.

The hypothesis to be tested can be formulated as:

$H_0: \mu_{\text{Treatment}} = \mu_{\text{Placebo}}$   
tested confirmatively against the alternative

$H_a: \mu_{\text{Treatment}} \neq \mu_{\text{Placebo}}$   
where  $\mu_{\text{Treatment}}$  is the change in biomarker relative to baseline in the treatment group, and  $\mu_{\text{Placebo}}$  is the change relative to baseline in the placebo group.

Table 7.7:1 Data of standard deviation over time in changes relative to baseline

Data of standard deviation over time in changes relative to baseline						
	CRPM		C1M		C3M	
	Placebo	Treatment	Placebo	Treatment	Placebo	Treatment
Study A						
Week 4	42% (n=100)	34% (n=143)	44% (n=116)	41% (n=176)	38% (n=116)	31% (n=176)
Week 16	33% (n=88)	36% (n=128)	42% (n=102)	58% (n=156)	32% (n=102)	27% (n=156)
Week 24	31% (n=83)	32% (n=131)	53% (n=97)	53% (n=162)	33% (n=97)	31% (n=162)
Study B						
Week 4	40% (n=71)	25% (n=66)	48% (n=76)	68% (n=75)	43% (n=71)	66% (n=67)
Week 12	43% (n=52)	47% (n=68)	45% (n=54)	55% (n=73)	44% (n=50)	44% (n=68)

Based on Table 7.7:1, sample sizes will be calculated for a range of common standard deviations of 30%; 40% and 50%.

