7.5.2 Other Secondary endpoints

The following secondary endpoints are defined:

- Rate of change (slope) in blood C1M from baseline to week 12
- Rate of change (slope) in blood C3M from baseline to week 12

Please refer to Section 7.3.2 of the CTP for further details of the analysis.

This endpoint will be analyzed in a similar manner as the primary endpoint. Reasonably, baseline CRPM as covariate will be replaced by baseline C1M and C3M in these analyses.

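### With 1:2 allocation, a primary slope model whose variances are not allowed to differ by arm can misstate the standard error of the treatment difference; estimate them by arm

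*Protocol*

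**What the plan says.** Protocol 7.3.1 analyses the CRPM slope over 12 weeks with a random coefficient regression. On the random effects it says "The intercepts and slopes will be assumed to be normally distributed with arbitrary covariance matrix". On the residual it says "The within patient error will be assumed to be independent and normally distributed with mean zero and a common variance". Neither sentence mentions treatment arm. Degrees of freedom come from Kenward-Roger, and alternative models for sensitivity analysis are left to the SAP.

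SAP 7.4.1 refers back to Protocol 7.3.1 and on to SAS code in Section 9.1, which is not in the public text. For C1M and C3M, SAP 7.5.2 says "This endpoint will be analyzed in a similar manner as the primary endpoint".

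Protocol 7.6 randomises patients "with an unequal probability 1 to 2 of assignment to nintedanib and placebo", and Protocol 7.7 plans 117 and 233. The sample size also works with one SD for both arms: "sample sizes will be calculated for a range of common standard deviations of 30%; 40% and 50" percent. That range is drawn from Table 7.7:1, which lists placebo and treatment SDs separately.

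**The concern.** A common variance is usually harmless at 1:1, because the pooled standard error of a difference is then right even when the arms differ in spread. At 1:2 this protection is lost. The pooled variance is dominated by the larger placebo arm, while the true variance of the difference is driven more by the smaller nintedanib arm. Kenward-Roger does not help: it adjusts inference within the covariance model it is given, and does not correct variances that were wrongly pooled.

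In Table 7.7:1, the only variance data in the plan, the arm SDs differ by up to 40/25 = 1.6-fold. A drug that acts on matrix turnover could change the spread of biomarker slopes as well as their mean. At stake is whether the test and interval for the slope difference keep their stated 5% and 95%, for CRPM and, through SAP 7.5.2, for C1M and C3M.

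**Working it through.** **The plan's own figure.** With SD s in both arms, difference d and 1:2 allocation, the nintedanib arm needs n = 10.507 × 1.5 × s²/d², where 10.507 = (1.960 + 1.2816)². For d = 20 and s = 30, 40, 50 this gives n = 35.5, 63.0, 98.5. Rounding up each arm gives totals of 107, 191 and 297; a noncentral-t calculation gives about 109, 191 and 298. Table 7.7:2 states 110, 192 and 299, so it is reproduced closely.

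**Reduction.** With complete visits at weeks 0, 4, 8 and 12, and covariates ignored, the slope test under one covariance structure is a pooled two-sample comparison of per-patient slopes. Write S_T and S_P for the arm SDs.

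- Pooled variance: V = (116·S_T² + 232·S_P²)/348
- Variance the model uses: V·(1/117 + 1/233)
- True variance: S_T²/117 + S_P²/233
- R = true variance / model variance
- Actual error = 2·[1 − Φ(1.96/√R)]; coverage is its complement

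At 1:1, R = 1 whatever the two SDs are.

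**Assumption.** The SD ratios in Table 7.7:1 carry over to the slopes. The documents do not establish this.

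**CRPM, Study B week 4 (40 v 25).** V = (116×625 + 232×1600)/348 = 1275. Model SE = √(1275 × 0.012839) = 4.05. True SE = √(625/117 + 1600/233) = 3.49. The model SE is 16% too large; R = 0.746 and the error is 2.3%.

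**CRPM, Study B week 12 (43 v 47).** V = 1969. Model SE = 5.03, true SE = √(2209/117 + 1849/233) = 5.18. The model SE is 3% too small; R = 1.061 and the error is 5.7%.

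**All rows.** The F-test compares the two SDs using the printed sample sizes and assumes normality.

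| Biomarker | Study, week | SD placebo | SD treatment | R | Actual error | F-test p |
|---|---|---|---|---|---|---|
| CRPM | A, 4 | 42 | 34 | 0.871 | 3.6% | 0.02 |
| CRPM | A, 16 | 33 | 36 | 1.059 | 5.7% | 0.39 |
| CRPM | A, 24 | 31 | 32 | 1.021 | 5.2% | 0.76 |
| CRPM | B, 4 | 40 | 25 | 0.746 | 2.3% | 0.0002 |
| CRPM | B, 12 | 43 | 47 | 1.061 | 5.7% | 0.51 |
| C1M | A, 4 | 44 | 41 | 0.954 | 4.5% | 0.40 |
| C1M | A, 16 | 42 | 58 | 1.231 | 7.7% | 0.0006 |
| C1M | A, 24 | 53 | 53 | 1.000 | 5.0% | 0.99 |
| C1M | B, 4 | 48 | 68 | 1.251 | 8.0% | 0.003 |
| C1M | B, 12 | 45 | 55 | 1.141 | 6.7% | 0.13 |
| C3M | A, 4 | 38 | 31 | 0.875 | 3.6% | 0.015 |
| C3M | A, 16 | 32 | 27 | 0.894 | 3.8% | 0.06 |
| C3M | A, 24 | 33 | 31 | 0.959 | 4.5% | 0.48 |
| C3M | B, 4 | 43 | 66 | 1.310 | 8.7% | 0.0005 |
| C3M | B, 12 | 44 | 44 | 1.000 | 5.0% | 0.99 |

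Six of the 15 rows differ at p < 0.05. The rows are not independent, but fewer than one would be expected by chance (15 × 0.05 = 0.75). Using a t critical value instead of 1.96 lowers the error figures by about 0.1 point.

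**Simulation.** In 60,000 two-sample trials per scenario, the pooled test had error 2.3% (40 v 25), 5.8% (43 v 47) and 8.4% (43 v 66). With separate variances it was 4.9%, 5.1% and 4.7%. This was done on patient slopes, not with the full mixed model.

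**Power at the planned difference.** For a 20-point CRPM difference with 117 and 233 patients, power is 97.5% pooled and 97.1% with separate variances at SDs 43/47. At 40/25 both exceed 99.9%.

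**The case against.** Four objections carry weight.

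- **The model is only partly visible.** The common-variance sentence covers the within-patient error alone. The slope covariance, which also enters the variance of a patient's slope, is called arbitrary with nothing said about arms. The SAS code is not public, and the SAP's contents list puts Section 7.4.1 on page 35 and Section 7.5 on page 39, so text on the primary endpoint is missing from what can be read. Arm-specific covariance cannot be ruled out. This stands, and it makes the point conditional.
- **The SDs are from elsewhere.** They describe percent change in rheumatoid arthritis patients, with the treatment not named, not slopes in ng/mL/month in IPF patients on nintedanib. This stands. They show that unequal spread is plausible, not that it will occur.
- **CRPM shows little risk of false positives.** In every CRPM row where treatment varies more, the ratio is at most 1.09 and equal SDs are not rejected. The 1.6-fold gap occurs once, at week 4, in the conservative direction. The 8.0% and 8.7% come only from week-4 rows for C1M and C3M. At week 12 no biomarker shows a significant difference. This stands.
- **A common covariance is a conventional default, so changing it is a preference.** This does not remove the point. At 1:2 a pooled variance misstates the standard error whenever the arm variances differ, and separate estimation costs almost nothing when they do not.

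A reader might also infer a loss of power. With 40 v 25 and a 10-point difference, power is about 72% pooled against 81% with separate variances. But the protocol does not plan for 10 points: "Sample size calculations are performed for assumed differences between treatment group and placebo of 20% and 30% difference".

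**Conclusion.** The plan as visible does not let variances differ by arm, and 1:2 allocation makes that choice matter. If the table's SD ratios applied to slopes, the actual error for CRPM would lie between 2.3% and 5.7%, so the main risk for the primary endpoint is an interval that is too wide. For C1M the range is 4.5% to 8.0% and for C3M 3.6% to 8.7%, with coverage as low as 91.3%. The week-12 rows, which match the endpoint's horizon, give 5.7%, 6.7% and 5.0%.

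A reader might conclude that the primary p-value and interval are wrong, or that the primary test is materially inflated. The documents support neither: the evidence is indirect, the model code is unseen, and no CRPM row gives more than 5.7%. The conclusion is that the standard error can be misstated and that the protection is cheap. The figures assume complete visits, no covariates, and SD ratios that transfer to slopes.

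**What to change.** Before unblinding, state in Protocol 7.3.1 and SAP 7.4.1/9.1 that the intercept and slope covariance matrix and the residual variance are estimated separately by treatment arm (in SAS, a GROUP option for treatment on the RANDOM and REPEATED statements), keeping Kenward-Roger. Name the common-covariance model as the prespecified fallback if the arm-specific model does not converge. Use the same model for C1M and C3M. If SAP 9.1 already does this, bring Protocol 7.3.1 into line with it.

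The cost is one option in the code, a sentence or two of text, and four extra parameters (a second intercept variance, slope variance, their covariance, and residual variance), which is negligible with 350 patients. There is a small risk of non-convergence, which the fallback covers. The timing matters because a variance model chosen after unblinding could be driven by the result.
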